## **OVEREAT Study Protocol**

### *Objective(s)*

The objectives of the present study are as follows:

- To examine the effects of high-fat overfeeding across a 7-day period, on circulating concentrations of the hepatokines LECT2, FGF21 and Fetuin-A.
- To examine the effects of high-fat overfeeding across a 7-day period, on subjective appetite, food preference and circulating concentrations of the appetite regulatory hormones Ghrelin and PYY.
- To observe whether changes in these variables occur alongside impairments in insulin sensitivity and glucose tolerance following seven days of high fat overfeeding.

### *Design*

The present study is a randomised, controlled, crossover design in which 12 recreationally active, healthy males will complete two week-long dietary conditions in a randomised order.

The two dietary conditions consist of a high-fat condition and a control condition. In the high-fat condition, participants will consume a diet comprising of 65% of total energy as fat and a total kilocalorie content equal to 150% of their estimated daily requirement. In the

control condition, participants' will consume their habitual diet as confirmed by a three-day food diary both before and during the control condition. The two diets will last seven days each with a three-week washout period separating the two conditions. An oral glucose tolerance test will be performed before and after the two diets to assess glycaemic control and hepatokine and appetite hormone responses will be measured across the seven days.

### *Methods*

#### Protocol

The participants will firstly undergo a prescreening visit to the laboratory in which written informed consent will be obtained. Further to this, participants will complete a health screen questionnaire, an international physical activity questionnaire and a food preference questionnaire in order to ensure compliance with the eligibility criteria and that the foods provided during the trial will be palatable. Anthropometrical measures will be then be taken including height, weight, waist circumference and body fat percentage (measured via bioelectrical impedance analysis). A finger prick blood sample will also be taken and fasting blood glucose concentrations will be analysed using a Cardiochek device in order to confirm normal fasting blood glucose levels as stated in the eligibility criteria. Prior to completing the prescreening session, participants will be set up with hip-based physical activity monitor (Actigraph) and a thigh-based sedentary behaviour monitor (ActivPAL) and instructed to wear the devices for seven days. Participants will then be provided with an activity diary to record periods where the devices are removed as well as a 3-day food diary (including two

week days and one weekend day) to complete. This will allow for a baseline assessment of the participants' habitual eating and activity habits.

After the completion of the 7-day physical activity and sedentary behaviour monitoring,

participants will be randomised to either the high-fat condition or the control condition.

Participants will attend the laboratory at 8:00 am for a pre-diet assessment following a 10-

hour overnight fast and having refrained from caffeine, exercise and alcohol in the prior 24

hours. Upon arrival, repeated written, informed consent will then be obtained and body

weight, body fat percentage and blood pressure will then be measured. Following this,

participants will be fitted with a mouth piece and their resting metabolic rate and fat

oxidation will be measured via indirect calorimetry using Douglas bags for expired gas

collection. Subjective ratings of appetite will then be measured using visual analogue scales

and food preference will be assessed using computer-based software (Leeds Food

Preference Questionnaire). A cannula will then be inserted into an antecubital vein for blood

sampling. A baseline blood sample (0 h) will be collected, followed by the commencement

of the oral glucose tolerance test. During this, participants will consume a solution

containing 75 g of glucose dissolved in 300 ml of water and further blood samples will be

taken at 0.5, 1, 1.5 and 2 h. The cannula will then be removed and the dietary condition will

commence upon leaving the laboratory. During the 7-day dietary period, participants will

undergo further monitoring of physical activity and sedentary behaviour, while during the

control condition; participants will also complete a 3-day food diary in order to confirm

maintenance of their habitual diet.

Both one day and three days after commencing the diets, participants will return to the

laboratory at 8:00am following a 10-hour overnight fast and having refrained from caffeine,

exercise and alcohol. Further repeat, written informed consent will be and measurements of body weight, blood pressure, subjective appetite and food preference will be obtained. A venous blood sample will then be collected via venepuncture to allow for the assessment of the time-course of changes in fasting circulating hepatokine and appetite hormone concentrations.

Upon completion of the 7-day dietary condition, participants will attend the lab the following morning at 8:00am following a 10-hour overnight fast and having refrained from caffeine, exercise and alcohol. Participants will undergo a post-diet assessment using the same procedures as the pre-diet assessment. A washout period of three weeks will then separate the two dietary conditions.

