School of Sport, Exercise and Health Sciences

Influence of High-fat Overfeeding on Circulating Hepatokine Concentrations: A Randomised Crossover Study

17th November 2017

OVEREAT Study Statistical Analysis Plan

The data collected will be analysed using the software package SPSS (SPSS Version 23, SPSS Inc., Chicago, IL) and an alpha value of $P < 0.05$ will be set to indicate statistical significance. Parametric assumptions will be checked using the Shapiro-Wilk test in order to confirm normal distribution of the data. Two-hour area under the curve (AUC) calculations for plasma glucose and insulin during the oral glucose tolerance tests will be performed using the trapezoidal method. Whole-body insulin sensitivity will be calculated using the Matsuda Insulin Sensitivity Index (ISI) equation:

$$\frac{10,000}{\sqrt{(\text{Glucose}_{0\text{ min}} \times \text{Insulin}_{0\text{ min}} \times \text{mean Glucose}_{\text{OGTT}} \times \text{mean Insulin}_{\text{OGTT}})}}$$

The homeostatic model assessment of insulin resistance (HOMA-IR) will also be calculated using the formula:

$$\frac{\text{Glucose}_{0\text{ min}} \times \text{Insulin}_{0\text{ min}}}{22.5}$$

Adipose tissue insulin resistance (ADIPO-IR) will be calculated using the formula:

$$\text{Insulin}_{0\text{ min}} \times \text{NEFA}_{0\text{ min}}$$

A one-way repeated measures analysis of variance (ANOVA) will be performed to assess differences in daily energy intake, daily fat intake and 7-day physical activity and sedentary behaviour (i.e sitting time, standing time, light physical activity, moderate-vigorous physical activity) between the high-fat condition, control condition and baseline measurement.

For the outcome measures which will be taken only pre- and post-dietary conditions, a 2×2 repeated measures ANOVA will be used for analysis. This includes the following outcome measures: Body fat percentage, resting metabolic rate, fat oxidation percentage, glucose AUC, insulin AUC and Matsuda ISI.

For the outcome measures which will be taken both pre-diet and post-diet as well as one and three days into the diet, a 2 x 4 repeated measures ANOVA will be used for analysis. This includes fasting plasma concentrations of: LECT2, FGF21, fetuin-A, acylated ghrelin, PYY, CTX, P1MP, glucose, insulin, NEFA and triglycerides. These outcome measures also include: HOMA-IR, ADIPO-IR, subjective ratings of appetite, food preference, body mass and both systolic and diastolic blood pressure.

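### Food intake on the day before the two pre-diet assessments is neither recorded nor replicated, which adds avoidable noise to the condition-by-time contrast in a 12-man crossover

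*Protocol*

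**What the plan says.** The trial is a crossover in which "12 recreationally active, healthy males will complete two week-long dietary conditions in a randomised order" (Protocol, Design).

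The order of events is in the Protocol subsection of Methods:

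- After a week of activity monitoring, "participants will be randomised to either the high-fat condition or the control condition".
- Next comes the first baseline visit: "Participants will attend the laboratory at 8:00 am for a pre-diet assessment". The same sentence requires a 10-"hour overnight fast and having refrained from caffeine, exercise and alcohol in the prior 24" hours.
- Dietary control begins only after the glucose tolerance test: "The cannula will then be removed and the dietary condition will" start as the participant leaves.
- After the first condition, "A washout period of three weeks will then separate the two dietary conditions". No dietary instruction is given for that interval.

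Food diaries appear in two places. The screening diary has a descriptive purpose: "This will allow for a baseline assessment of the participants' habitual eating and activity habits". A second three-day diary falls within the control week and confirms that the habitual diet was kept. The Design section speaks of diaries before and during the control condition. None is tied to the day before a pre-diet visit, and none is to be repeated.

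The SAP treats the pre-diet value as one level of time. It is one of two levels in the 2×2 repeated measures ANOVA (body fat, resting metabolic rate, fat oxidation, glucose and insulin AUC, Matsuda index). It is one of four in the 2×4 ANOVA (hepatokines, appetite hormones and other fasting outcomes). Post hoc paired tests follow a significant interaction. No check of, or adjustment for, previous-day intake is planned.

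**The concern.** The Protocol treats the 24 hours before a baseline visit as worth standardising, yet leaves out food in a trial whose exposure is food. A participant may eat quite differently on the days before his two baselines, and nothing in the plan would reveal it.

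In a crossover, stable differences between men cancel. What limits precision is variation within a man from visit to visit. Any part of that variation due to the previous day's food, at either pre-diet visit, passes straight into the comparison of the two conditions. With 12 participants and no sample-size justification, precision is scarce. Intake cannot be matched once the visits are over, so this has to be settled in the protocol.

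**Working it through.** **Planned figure.** Neither document gives a standard deviation, an effect size or a power calculation, so there is nothing to reproduce.

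**Inputs from the documents.** n = 12, two conditions (Protocol, Design). A P value below 0.05 "will be set to indicate statistical significance" (SAP). The gap between the pre-diet visits is 7 days of diet plus 3 weeks of washout, about 4 weeks.

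**Assumptions.** Equal, independent within-person variance s² at each visit. A share f of s² comes from the previous day's intake; f = 0.2 to 0.4 is a working range with no source in the documents.

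**Step 1: the contrast.** In the 2×2 ANOVA the interaction test equals a paired t-test on 11 degrees of freedom of

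D = (post − pre, high-fat) − (post − pre, control).

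Four visits contribute, so Var(D) = 4s². The two pre-diet visits supply 2s².

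**Step 2: perfect matching.** If the previous-day component is the same at both pre-diet visits it cancels, and Var(D) = (4 − 2f)s². The standard error falls by 1 − √((4 − 2f)/4).

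| f | Var(D) | Variance cut | SE cut |
|---|---|---|---|
| 0.2 | 3.6s² | 10% | 1 − √0.9 = 5.1% |
| 0.4 | 3.2s² | 20% | 1 − √0.8 = 10.6% |

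In terms of variance, 12 matched men would give the precision of 12/0.9 = 13.3 to 12/0.8 = 15 unmatched men.

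**Step 3: imperfect matching.** If the previous-day components at the two visits correlate only r, then Var(D) = (4 − 2rf)s². With r = 0.5 the SE cut is 1 − √0.95 = 2.5% at f = 0.2 and 1 − √0.9 = 5.1% at f = 0.4.

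**Step 4: a second parameterisation.** Let σ be the within-person SD per visit, and let previous-day intake add an SD of τ at the two pre-diet visits only. The SE of D is multiplied by √(1 + τ²/(2σ²)). Take an effect of 0.889 SD of D, which has 80% power at n = 12 with no added noise (two-sided 5%, exact noncentral F).

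| τ/σ | SE multiplier | Power |
|---|---|---|
| 0.25 | 1.02 | 78.8% |
| 0.5 | 1.06 | 75.3% |
| 0.75 | 1.13 | 69.8% |
| 1.0 | 1.22 | 63.0% |

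**Scope.** These figures describe the 2×2 contrast. They do not describe the 2×4 omnibus interaction used for the hepatokines and appetite hormones. Pre-diet noise enters that test too, but as one of four time levels, and its cost is not computed here.

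**The case against.** Three stronger readings are tempting, and the documents do not support them.

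- **The baseline is uncontrolled.** It is not. Time of day, fasting, caffeine, exercise and alcohol are all set. Only the previous day's food is left open.
- **The day-1 sample shows that the plan believes one day of diet moves these markers.** Sampling on day 1 tests for an early change and presumes none. That day is also 150% of estimated energy at 65% fat, so it says little about ordinary variation in a habitual diet.
- **Men eat differently before the high-fat week, so the contrast is biased.** The Protocol says when participants are randomised, not when they are told. Nothing indicates that eating changes or in which direction. A shift at the high-fat baseline alone would pass one-for-one, with opposite sign, into D. Shifts of 0.5σ and 1.0σ would raise the false-positive rate from 5% to 12.4% and 35.3%. Those shifts are invented to show the mechanism and do not estimate anything in this trial.

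It is also fair to say that baselines on a habitual diet suit a comparison of overfeeding with habitual eating. That the high-fat post-diet visit follows provided food is the intervention, not a defect. The 20–40% share is unsupported, and replication from a record is never perfect. The day before the control post-diet visit would still vary.

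These points limit the claim to precision and make its size uncertain. They do not close the gap: no passage records or matches intake on the day before either pre-diet visit.

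**Conclusion.** The concern holds as a matter of precision. Previous-day food intake is left free before two baselines about four weeks apart, and both baselines sit inside the tested interaction. For the 2×2 outcomes the avoidable loss is about 5–11% of the standard error if previous-day intake explains 20–40% of within-person visit variance and replication is perfect. It is about half that if the replicated intake matches only in part (r = 0.5). The documents give no data with which to narrow this range, and the figure should not be carried over to the 2×4 tests.

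Unsystematic variation of this kind costs power and does not bias the estimate. A systematic difference between the two baselines remains a possibility that the documents neither establish nor rule out. The change is worth making because it is cheap and cannot be made afterwards.

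**What to change.** Add to the Protocol subsection of Methods:

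1. Each participant records all food and drink in the 24 hours before the first pre-diet visit.
2. He receives a copy and repeats that intake in the 24 hours before the second pre-diet visit.
3. Staff check the repeat against the copy on arrival and note departures, so that adherence can be reported.

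As a minor addition, tell the participant his first condition only once the first pre-diet assessment is finished. This is feasible because the diet starts on leaving the laboratory. It protects that visit only, since the second condition is then known by elimination; replication is therefore the main measure.

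The cost is a one-day record, a copy, a short check and a small burden on participants. No extra men, visits or assays are needed, and neither study diet changes.

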### Diet

During the high-fat dietary condition, all foods will be provided to the participants and will contain an energy content of 50% extra kilocalories above the participants' daily energy requirement and a dietary fat composition of 65%. The participants' daily energy requirement will be estimated using the Mifflin equations and subsequently multiplied by a physical activity correction factor of 1.7 and a thermogenic effect of feeding correction factor of 1.1. The foods provided will be primarily high in saturated fats and participants will be told to consume all foods provided within the study and no other calorie-containing foods or drink. In the event of any leftover food, participants will be told to bring in the food for weighing and subsequent subtraction from the calculated intake. Furthermore, participants will be told to fry foods where applicable and to minimise fat wastage during

the cooking process. During the control condition, participants will be told to consume their habitual diet, which will be confirmed using the 3-day food diaries. In addition to this, participants will be told on both diets to maintain their normal activity habits which will be confirmed by the physical activity and sedentary behaviour monitoring.

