Where a significant interaction effect is observed, *post hoc* paired samples *t*-tests with a Bonferroni correction will be used to locate any differences. If Mauchly's test of sphericity is violated by any variables, Greenhouse-Geisser corrected values will be used.

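### Maintained activity is to be confirmed by monitoring, but the SAP plans only a three-level difference test and no estimate of the high-fat minus control change

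*Protocol*

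**What the plan says.** The Protocol (Design) states that "12 recreationally active, healthy males will complete two week-long dietary conditions" in random order. Under Diet, men on both diets are told to "maintain their normal activity habits which will be confirmed by the physical activity and sedentary behaviour monitoring".

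The SAP gives one analysis of the monitoring data: "A one-way repeated measures analysis of variance (ANOVA) will be performed to assess differences in daily energy intake", fat intake and activity, with the comparison made "between the high-fat condition, control condition and baseline measurement". The activity measures named are "sitting time, standing time, light physical activity, moderate-vigorous physical activity". The significance level is 0.05.

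The SAP's closing paragraph provides Bonferroni-corrected paired t-tests, but on a condition: "Where a significant interaction effect is observed". Neither document gives a tolerance, a confidence interval or any other criterion by which activity would count as maintained.

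**The concern.** The Protocol's aim is a statement of no change, and the planned analysis is a test for change. Such a test can show that activity moved. When it is not significant, it does not show that activity stayed put, least of all with 12 men.

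The test is also not aimed at the contrast that matters. For interpreting the diet comparison, the useful quantity is the difference in activity between the high-fat and control weeks. The omnibus F mixes that contrast with two others involving baseline. Because the post hoc rule needs an interaction, nothing in the plan separates them, even after a significant result.

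What is at stake is interpretation. If men sat more or exercised less while overfed, part of any change in insulin sensitivity, glucose tolerance or appetite could run through activity. The report should be able to say how large such a change could have been.

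**Working it through.** The documents contain no power calculation, so there is no figure of theirs to reproduce.

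**Inputs from the documents**
- n = 12 (Protocol, Design); complete monitoring in all 12 is assumed.
- k = 3 levels and alpha = 0.05 (SAP).
- Degrees of freedom: k − 1 = 2 and (k − 1)(n − 1) = 2 × 11 = 22. The critical value of F(2,22) is 3.44.

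**Inputs assumed, because the documents give none**
- A shift of 0.5 SD, on two alternative scales: the SD of the within-man difference, or the between-man SD with a within-man correlation ρ.
- Sphericity.

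**Formula.** The noncentrality is λ = n × Σ(μj − mean μ)² / σe². The miss rate is the probability that a noncentral F(2, 22, λ) falls below 3.44.

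**Scale 1: SD of the within-man difference set to 1, so σe² = 1/2**
- Only the high-fat week shifted, means (0, 0, 0.5): the sum of squares is 0.0278 + 0.0278 + 0.1111 = 0.1667. λ = 12 × 0.1667 / 0.5 = 4.0. Power is 0.368, so the miss rate is 63%.
- Control halfway, means (0, 0.25, 0.5): the sum of squares is 0.0625 + 0 + 0.0625 = 0.125. λ = 12 × 0.125 / 0.5 = 3.0. Power is 0.285, so the miss rate is 72%.
- As a cross-check, a two-sided paired t-test on 11 df with noncentrality 0.5 × √12 = 1.73 has power 0.353, a miss rate of 65%.

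**Scale 2: between-man SD set to 1, so σe² = 1 − ρ**

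With only the high-fat week shifted, λ = 12 × 0.1667 / (1 − ρ) = 2 / (1 − ρ).

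| ρ | λ | Miss rate |
|---|---|---|
| 0 | 2.0 | 80% |
| 0.5 | 4.0 | 63% |
| 0.7 | 6.7 | 43% |
| 0.8 | 10 | 24% |
| 0.9 | 20 | 3% |

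**Precision of the paired difference.** The 95% half-width is t(0.975, 11) / √12 = 2.201 / 3.464 = 0.64 SD of the paired difference, taking the sample SD equal to the true one.

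**Would a formal equivalence rule work?** Suppose the true shift is zero and a 90% confidence interval must lie inside a margin. With 12 men, simulation gives success in about 11% of trials for a margin of 0.5 SD of the paired difference, 57% for 0.75 SD and 89% for 1.0 SD. These margins are illustrative; the documents offer none.

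**The case against.** **No decision rule is written.** A reader might infer that the plan will treat a non-significant F as proof of unchanged activity. The documents do not say so. The SAP says only that the ANOVA assesses differences, and the Protocol speaks of confirmation by monitoring, not by a P value. The same Diet paragraph uses that verb for the food diaries, so it may be ordinary compliance language. This stands. What remains is that no other criterion is offered.

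**The miss rate depends on the scale.** It would be tempting to say flatly that a half-SD shift is missed two times in three. That holds on the within-man difference scale, or for a between-man SD with correlation near 0.5. If weekly activity is highly correlated within men, the test is much more sensitive. Nor do the documents show that 0.5 SD is a material number of minutes. This stands too.

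**Four measures are tested.** If all four shifted by 0.5 SD of the within-man difference, the chance that every test misses lies between about 16% (0.632⁴, if independent) and 63% (if perfectly correlated). So 63% describes one measure and is the upper end for a broad shift.

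**Baseline may differ by design.** Men refrain from exercise before the repeated laboratory visits in both diet weeks, and no such visits are described for the baseline week. The F test might therefore be significant with no difference between the diets, so non-significance cannot be called the likely result. This does not rescue the test: it is one more reason to isolate high-fat minus control.

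**The diet comparison is not biased.** A reader might infer that an undetected activity change would invalidate the diet effect. It would not. Order is randomised, and a change caused by overfeeding is a consequence of the assigned condition. It complicates the mechanism and leaves the overall effect valid.

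**Conclusion.** The point holds as a gap in analysis and wording. The plan promises confirmation of unchanged activity, specifies only an omnibus difference test in 12 men, and provides no estimate of the one contrast that bears on the diet comparison. That conclusion does not depend on any assumed SD.

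The size does depend on one. For a shift confined to the high-fat week and equal to 0.5 SD of the within-man difference, a single measure's test misses it in about 63% of trials, and in 72% if control lies halfway. On the between-man scale the range is about 80% to 3% as the correlation goes from 0 to 0.9. All figures assume 12 complete records and sphericity.

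The severity is minor. Activity is not among the stated objectives, and no outcome analysis or sample size changes.

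**What to change.** In the SAP, for sitting, standing, light and moderate-vigorous time:
- Report the mean paired high-fat minus control difference in min/day with a 95% confidence interval.
- Keep the one-way ANOVA as description.
- State that a non-significant F will not be taken as evidence that activity was maintained, and that the report will instead describe the size of change the interval leaves open.

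In the Protocol, under Diet, replace 'confirmed' with 'assessed' for activity.

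A formal equivalence margin should not be required. The documents supply none, and at 12 men a margin of 0.5 SD would usually fail even with no true change.

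The cost is a few lines of text and one interval per measure; no new data are needed. The drawback is that the statement on activity will often be less favourable, because an interval extending about 0.64 SD of the paired difference either side of the estimate will often leave moderate changes open.
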